11.5.7 Subgroup Analyses

Primary and secondary efficacy variable summaries will be repeated for the following subgroups if sample size allows **by study visit using OC data**:

- Gender: male and female
- Age groups: 9 to 17 years and ≥ 18 years
- Race: white, African-American/Black, other
- Body mass index: $< 25 \text{ kg/m}^2$ and $\geq 25 \text{ kg/m}^2$
- Baseline acne severity (IGA score): moderate and severe
- Oral contraceptive use in females: female subjects who use oral contraceptives versus female subjects who do not

11.6 Safety Analyses

11.6.1 Adverse Events

Treatment-emergent adverse events will be classified into a standardized terminology using the Medical Dictionary for Regulatory Activities (MedDRA) system organ classifications and preferred terms. Adverse events with onset on or after the first dose date of test or reference article and prior to or on study completion will be considered as “treatment-emergent.”

Although a preferred term or system organ class may be reported more than once for a subject, each subject will only be counted once in the incidence count for that preferred term or system organ class for each particular summary. Summaries of safety data will be generated for the following summary types:

- Overall summaries
- Summaries by MedDRA system organ class, MedDRA preferred term, test or reference article relationship, and severity.
- Summaries by MedDRA preferred term and test or reference article relationship in descending order.
- Summaries of serious adverse events by MedDRA preferred term and test or reference article relationship in descending order.
- Summaries of adverse events by MedDRA system organ class, MedDRA preferred term, and test or reference article relationship for the primary events leading to premature discontinuation from the study.

These summaries will present the number and percentage of subjects reporting an adverse event by treatment and overall as well as the number of events reported. The denominators for calculating the percentages by treatment will be based on the number of subjects exposed in the Safety population to each treatment and overall. The treatment will be based on the **double-blind** treatment received. **For subjects who are in PK Schedule 3, the treatment-emergent adverse event summary described above will comprise data prior to the active dose taken at the Week 12 visit. Further adverse events experienced after this Week 12 dose will be listed separately for these subjects.**

11.6.2 Extent of Exposure

The number of doses taken and the duration of exposure to study drug will be summarized by treatment using descriptive statistics for the Safety population. Duration of exposure will be calculated as the difference between the last **double-blind** dose date and the first dose date plus one day.

Additionally, these summaries will present the number and percentage of subjects for each interval (1 week multiples) of total exposure in each treatment. The denominators for calculating the percentages will be based on the number of subjects with exposure for each treatment.

11.6.3 Clinical Laboratory Evaluations

Continuous clinical laboratory analytes will be summarized by **double-blind** treatment, analyte, and visit using descriptive statistics. Categorical laboratory analytes, classified as normal or abnormal, will be summarized by treatment analyte, and visit using the number and percentage of subjects in each category. The denominators for calculating the

percentages will be based on the number of subjects in each treatment with non-missing assessments at a particular visit for the Safety population.

Shifts to values outside of the normal range will be presented by treatment and analyte and will be summarized by the number and percentage of subjects with evaluable shifts. An evaluable shift is one where both the Screening Visit value and the on-treatment value or early termination value are recorded. The denominators for calculating the percentages will be based on the number of subjects in each treatment group who have an evaluable shift for a particular analyte.

11.6.4 Electrocardiograms

Electrocardiographic evaluations and shifts will be presented by visit and **double-blind** treatment. Evaluations will be summarized by the number and percentage of subjects for each interpretation and shift category. The denominators for calculating the percentages will be based on the number of subjects with assessments in each treatment for the Safety population.

11.6.5 Vital Signs

Vital sign measurements will be summarized for the Safety population by **double-blind** treatment and visit using descriptive statistics. Additionally, descriptive statistics will be presented by treatment and day for the CFB for vital signs. The baseline values will be defined as the last value collected prior to the first dose of the study drug.

11.7 Other Assessments or Analyses

Other study assessments listed below will be summarized or provided in data listings as specified in the statistical analysis plan.

11.7.1 Demographics and Baseline Characteristics

Subject demographic and physical characteristic data will be summarized by treatment and overall for each analysis population using descriptive statistics (mean, median, 25th percentile, 75th percentile, SD, SEM, minimum, maximum, and number of subjects) for continuous variables and frequency distributions (counts and percentage of subjects) for categorical variables.

Medical history items will be coded using standardized terminology from the MedDRA system organ classifications and preferred terms. Medical history will be summarized using counts and percentages of subjects in each system organ class and preferred term by treatment and overall for the Safety population.

11.7.2 Medications

Medication usage will be coded using the World Health Organization (WHO) Drug Dictionary. Medications will be presented by WHO Drug Anatomical/Therapeutic/Chemical

category and WHO Drug preferred name. Summaries will be presented for prior (prior to the first treatment period) medication use and concomitant (after first treatment has been given) medication use. Medications with an end date occurring before the first study drug dose date in the treatment period will be identified as prior medications. Medications with a start date occurring on or after the first study drug dose date in the treatment period or medications with a start date prior to the first dose that are on-going or with end dates that are on or after the first treatment start date will be identified as concomitant medications.

All summaries will present the number and percentage of subjects for each medication by treatment and overall. The denominators for calculating the percentages will be based on the number of subjects in the Safety population for each treatment and overall.

11.7.3 Compliance

Compliance will be assessed by comparing the expected number of doses taken, based on the total number of treatment days within each visit and within the entire treatment period of the study, with the number of returned doses to the clinic at the end of each treatment visit. Treatment compliance will be calculated for each subject/visit and over all visits for the Safety population. Compliance values that are less than 0% will be set to 0%. Summaries will be presented using descriptive statistics for the Safety population.

$$\text{Compliance} = \left[\frac{\# \text{ Dispensed} - \# \text{ Returned}}{\# \text{ Expected to be used}} \right]$$

11.7.4 IGA for Non-facial Sites

IGA scores for neck, chest, and back sites will be summarized by visit and treatment using counts and percentages for each site.

11.7.5 Noninflammatory Lesion Counts

There will be no statistical testing for absolute CFB in noninflammatory lesion counts at Week 12; however, descriptive summaries will be provided including 95% CIs for each treatment and for the treatment difference using an ANCOVA model with the baseline value as a covariate and additional terms included to represent effects of treatment and (pooled) site with OC visit data and the ITT population.

11.7.6 Skindex Questionnaire

Scoring, scaling, and the handling of missing data will be handled in accordance with the recommendations accompanying the Skindex-16 and will be described in more detail in the Statistical Analysis Plan. Descriptive summaries will be provided for the ITT population for scale scores and total score by treatment and visit. Additionally, CFB for scale and total scores will be provided for each treatment. Change from baseline in scale and total scores will be analyzed using an ANCOVA model with the baseline value as a covariate and additional terms included to represent effects of treatment and (pooled) site. Analyses will be provided for the ITT population. The adjusted means with associated 95% CIs from the

ANCOVA model will also be presented for each treatment and for the difference between the treatments.

11.7.7 Photographs

No statistical summaries based on photographic images are planned for the clinical study report.

11.7.8 Pharmacokinetics

Individual sarecycline and R-sarecycline plasma concentrations will be listed.

Sarecycline plasma concentration data obtained in the study will be utilized to estimate population PK parameters using nonlinear mixed-effects modeling (NONMEM). The effects of covariates on PK parameters will be evaluated as part of the analysis. The analysis will be described in a separate analysis plan.

12 DOCUMENTATION REQUIREMENTS AND RECORDKEEPING

12.1 Source Documentation

The CRFs represent a record of the subject's experience in the study, therefore, the CRF data must be supported by original (or source) medical records, as appropriate. CRF data recorded directly into the CRF is also considered source data when there are no other written or electronic records preceding the CRF entry.

Prior to enrolling a subject in the study, the Investigator must document his/her review of subject eligibility criteria in the source records for the subject, including the Investigator's signature and date on any medical and laboratory reports indicating a review of the source data occurred. The Investigator will continue to follow this practice for any subsequent medical and laboratory reports generated as a result of the clinical study.

The Investigator agrees that the Sponsor or its designated agents, the IRB, the FDA or foreign regulatory agencies will have reasonable access to study source documentation for purposes of audit and monitoring visit review both during and after completion of the study. Monitoring visits provide the Sponsor with the opportunity to evaluate the progress of the study; to verify the accuracy and completeness of CRFs; to ensure that all protocol requirements, applicable regulations and Investigator's obligations are being fulfilled; and to resolve any inconsistencies in the study records. All participating subjects will be required to signify their approval to permit inspection of their medical records by representatives of Sponsor, the IRB, the FDA and/or foreign regulatory agencies, as needed.

12.2 Data Capture and Discrepancy Management

Site personnel will be responsible for the completion and correction of CRFs according to the protocol and other instructions provided by the Sponsor or their designee. The Investigator is responsible for ensuring the completeness and accuracy of the data as evidenced by the Investigator's signature and date once the subject has completed the study and all required study data has been entered into the CRF.

Since site personnel will enter data directly into a validated electronic CRF, programmatic data validation procedures will be employed to identify data discrepancies to site personnel at the time of entry and/or upon saving the data. Designated site personnel will resolve any discrepancies via the electronic CRF. Any additional findings upon clinical review by the Sponsor or their designee will be entered into the system for review and resolution by site personnel. A full audit trail of data changes following entry will be captured during the study in the electronic data management system. The Investigator will be provided with a copy of all CRF data for retention.

13 OTHER INFORMATION

13.1 Financing and Insurance

Financing and insurance is addressed in a separate agreement.

13.2 Publication and Disclosure Policy

Publication and disclosure policy is addressed in a separate agreement.

13.3 Termination of the Study

If the study is terminated prematurely or suspended, the appropriate IRB and regulatory authority(ies) will be promptly informed of the termination or suspension and will be provided the reason(s) for the termination or suspension. All obligations and responsibilities of the Sponsor and the Investigator under GCP, the US CFR and the Declaration of Helsinki will remain in force if the study is terminated prematurely.

15 APPENDICES

Appendix 1 Study Schedule of Events

Appendix 2 Clinical Laboratory Evaluations

Appendix 3 Collection, Processing, Storage and Shipment Instructions for PK Samples

Appendix 4 Skindex Questionnaire

Appendix 5 Investigator Signature

Appendix 6 Sponsor Signatures

Appendix 1 Study Schedule of Events

	Screening Period		Treatment Period					
	SV1	SV2 (Baseline Assessment)	Telephone Contact Week 1 ± 3 d	Visit 1 Week 3 ± 3 d	Visit 2 Week 6 ± 3 d	Visit 3 Week 9 ± 3 d	Visit 4 Week 12 /ET ± 3 d	Visit 5 ^d Week 13 /ET ± 3 d
Informed Consent	X							
Assign Subject Number using the IRT	X							
Inclusion/Exclusion	X	X						
Demographic Data	X							
Medical/Surgical History	X							
Physical Examination	X	X ^a					X	X
Height & Weight	X	Weight only					Weight only	Weight only
Vital Signs	X	X		X	X	X	X	X
Hematology, Serum Chemistry, Urinalysis and Lipids	X	X ^b		X			X	
TSH, Free T4 and T3	X						X	
Urine pregnancy test	X	X		X	X	X	X	X
ECG	X						X	
Facial Investigator's Global Assessment		X		X	X	X	X	
Facial Lesion Counts		X		X	X	X	X	
Facial Photographs		X		X	X	X	X	

	Screening Period		Treatment Period					
	SV1	SV2 (Baseline Assessment)	Telephone Contact Week 1 ± 3 d	Visit 1 Week 3 ± 3 d	Visit 2 Week 6 ± 3 d	Visit 3 Week 9 ± 3 d	Visit 4 Week 12 /ET ± 3 d	Visit 5 ^d Week 13 /ET ± 3 d
Non-facial Investigator's Global Assessment		X		X	X	X	X	
Skindex Questionnaire		X					X	
Dispense Diary for Subjects Participating in PK Sampling		X				X		
PK Blood Sample Collection for PK 1, PK 2, and PK 3 ^c				X			X	
Review and Collect Diaries				X			X	
Randomization		X						
Dispense Study drug		X		X	X	X	X ^d	
Study drug Accountability /Compliance			X	X	X	X	X	
Concomitant Medication Use	X	X		X	X	X	X	X
Adverse Events	X	X	X	X	X	X	X	X

ECG= electrocardiogram; ET= End of treatment; X^a: Only for subjects requiring medication/therapy washout; X^b: Re-draw blood and urine samples for clinical laboratory evaluations only if washout duration exceeded 5 weeks. ^c PK Schedule 1, PK Schedule 2, or PK Schedule 3 should be performed at selected sites based on what the subject chose in the ICF, ^dFor subjects participating in PK Schedule 3 only.

Appendix 2 Clinical Laboratory Evaluations

Hematology

Hemoglobin	Mean cell volume
Hematocrit	White blood cell & Differential
Red blood cell count	Platelet count

Serum Chemistry

Albumin	Total protein
Alanine aminotransferase	Serum creatinine
Aspartate aminotransferase	Sodium
Blood urea nitrogen	Potassium
Gamma glutamyl transferase	Calcium
Glucose	Chloride
Lactate dehydrogenase	Bicarbonate
Total bilirubin	Phosphorus
Creatine phosphokinase	

Urinalysis

Color	Protein
Specific gravity	Glucose
Potential for hydrogen (pH)	Blood
Leukocytes	Bilirubin
Ketones	

Lipid Profile

Total cholesterol	Triglycerides
-------------------	---------------

Thyroid Function

Thyroid stimulating hormone	Free T4 and T3
-----------------------------	----------------

Other

Urine pregnancy test

**Appendix 3 Collection, Processing, Storage and Shipment
Instructions for PK Samples**

Follow detailed instructions as per the PK Laboratory manual.

The study includes a screening period of up to 35 days to establish eligibility and baseline conditions followed by a 12-week treatment period. Eligible subjects will be randomized in a 1:1 ratio to receive daily oral doses of either 1.5 mg/kg sarecycline tablets or placebo tablets. Subjects will return to the clinic on an outpatient basis following 3, 6, 9 and 12 weeks of treatment. At each clinic visit, facial acne will be evaluated through lesion counts and Investigator's Global Assessment (IGA) scores by visual inspection; non-facial inflammatory acne will also be evaluated by IGA of the neck, chest and back. The co-primary efficacy endpoints of the study are the absolute change from baseline in the facial inflammatory lesion count at Week 12 and a dichotomized IGA (dichotomized to reflect either 'success' or 'failure' with 'success' defined as at least a 2-point decrease from baseline in the IGA assessment and a score of clear [0] or almost clear [1] on the IGA assessment) at Week 12. Safety evaluations (adverse events, vital signs, clinical laboratory evaluations, electrocardiograms (ECG) and physical examinations) will be conducted at specific treatment period visits and at study termination.

The study drug, referred to as investigational product in this statistical analysis plan, quantity and dispensing schedule for this study are as follows:

Visit	Quantity Dispensed
Screen Visit (SV) 2	30
1	30
2	30
3	30

The schedule of evaluations for Study SC1401 is presented in Table 4-1.

Table 4–1. Study Schedule of Events: Study SC1401

	Screening Period		Treatment Period					
	SV1	SV2 (Baseline Assessment)	Telephone Contact Week 1 ± 3 d	Visit 1 Week 3 ± 3 d	Visit 2 Week 6 ± 3 d	Visit 3 Week 9 ± 3 d	Visit 4 Week 12 /ET ± 3 d	Visit 5 ^d Week 13 /ET ± 3 d
Informed Consent	X							
Assign Subject Number using the IRT	X							
Inclusion/Exclusion	X	X						
Demographic Data	X							
Medical/Surgical History	X							
Physical Examination	X	X ^a					X	X
Height & Weight	X	Weight only					Weight only	Weight only
Vital Signs	X	X		X	X	X	X	X
Hematology, Serum Chemistry, Urinalysis and Lipids	X	X ^b		X			X	
TSH, Free T4 and T3	X						X	
Urine pregnancy test	X	X		X	X	X	X	X
ECG	X						X	
Facial Investigator's Global Assessment		X		X	X	X	X	
Facial Lesion Counts		X		X	X	X	X	
Facial Photographs		X		X	X	X	X	
Non-facial Investigator's Global Assessment		X		X	X	X	X	

Table 4–1. Study Schedule of Events: Study SC1401

	Screening Period		Treatment Period					
	SV1	SV2 (Baseline Assessment)	Telephone Contact Week 1 ± 3 d	Visit 1 Week 3 ± 3 d	Visit 2 Week 6 ± 3 d	Visit 3 Week 9 ± 3 d	Visit 4 Week 12 /ET ± 3 d	Visit 5 ^d Week 13 /ET ± 3 d
Skindex Questionnaire		X					X	
Dispense Diary for Subjects Participating in PK Sampling		X				X		
PK Blood Sample Collection for PK 1, PK 2, and PK 3 ^c				X			X	
Review and Collect Diaries				X			X	
Randomization		X						
Dispense Study drug		X		X	X	X	X ^d	
Study drug Accountability /Compliance			X	X	X	X	X	
Concomitant Medication Use	X	X		X	X	X	X	X
Adverse Events	X	X	X	X	X	X	X	X

ECG= electrocardiogram; ET= End of treatment; X^a: Only for subjects requiring medication/therapy washout; X^b: Re-draw blood and urine samples for clinical laboratory evaluations only if washout duration exceeded 5 weeks. ^c PK Schedule 1, PK Schedule 2, or PK Schedule 3 should be performed at selected sites based on what the subject chose in the ICF, ^dFor subjects participating in PK Schedule 3 only.

5.0

OBJECTIVES

The primary objective is to evaluate the efficacy of oral sarecycline 1.5 mg/kg/day compared to placebo in treating inflammatory acne lesions in subjects with moderate to severe facial acne vulgaris based on Investigator's Global Assessment score and inflammatory lesion counts.

The secondary objectives are to evaluate the safety of oral sarecycline 1.5 mg/kg/day based on adverse events, vital signs, electrocardiograms, physical examinations and clinical laboratory tests.

6.0**ANALYSIS POPULATIONS AND DATASETS****6.1****SCREENED POPULATION**

The Screened Population will consist of all subjects who underwent a Screening Visit 1 and received a subject identification number (SID).

6.2**SAFETY POPULATION**

The Safety Population will consist of all subjects who received at least one dose of investigational product. All summaries of this population will be based on the treatment group each subject actually received.

6.3**INTENT-TO-TREAT POPULATION**

The Intent-to-Treat (ITT) Population will consist of all randomized subjects. All summaries of this population will be based on the treatment group each subject was randomized to receive.

6.4**PER-PROTOCOL POPULATION**

Per-protocol (PP) population will consist of all subjects in ITT population, as defined below. All summaries of this population will be based on the treatment group each subject was randomized to receive.

Subjects with the following conditions will be excluded from the PP population:

1. Did not meet inclusion/exclusion criteria
2. Have taken any interfering concomitant medications
3. Duration of treatment less than 68 days, or did not complete study based on subject exit status, or overall study drug compliance less than 80%
4. Received treatment different from the assigned treatment

A list of subjects with conditions 1, 2, and 3 above prior to unblinding will be created. This list will be reviewed by a Clinical Representative to determine which subjects are to be excluded from the PP population. These subjects will then be documented in a signed memo prior to unblinding. The subjects who received treatment different from the assigned treatment (condition 4) will be identified after unblinding and will be documented in a separate signed memo.

Three “visit types” will be defined for the purposes of analysis and summaries:

- Observed Cases (OC) – includes assessments collected at each scheduled visit. All applicable efficacy and safety variables will be summarized for OC visits.

- Multiple Imputation Data – for the primary and secondary efficacy endpoints, missing data will be imputed using multiple imputation procedures further described in Section 16.2.
- LOCF – defined as the last post-baseline data recorded for each efficacy variable. This visit will be denoted as Week 12 (LOCF) and will only be used to summarize efficacy data. The LOCF visit provides missing value imputation for subjects who do not provide data for the Week 12 visit.

7.0 SUBJECT DISPOSITION

The number and percentage of subjects in 3 of the study populations (Safety, ITT and PP) will be summarized by treatment group and study center; the Screened Population will be summarized overall only by study center.

Screen-failure subjects (ie, subjects screened but not randomized) and the associated reasons for failure to randomize will be tabulated overall for the Screened Population. The number and percentage of subjects who complete the treatment period and of subjects who prematurely discontinue during the same period will be presented for each treatment group and pooled across treatment groups for the ITT Population. The reasons for premature discontinuation from the treatment period as recorded on the termination pages of the electronic case report forms (eCRF) will be summarized (number and percentage) by treatment group for the ITT Population. All subjects who prematurely discontinue during the treatment period will be listed by discontinuation reason for the ITT Population.

All subjects who are in ITT Population but not in PP Population will be listed with reasons provided.

8.0

DEMOGRAPHICS AND OTHER BASELINE CHARACTERISTICS

Demographic parameters (age; age group (≥ 9 years and < 18 years vs. ≥ 18 years); age group (≥ 9 years and < 12 years, ≥ 12 years and < 18 years, and ≥ 18 years); race; sex; weight; weight group (33 to 54 kg, 55 to 84 kg, and 85 to 136 kg), height; body mass index (BMI), calculated as weight [kg]/(height [m]²; BMI group (< 25 kg/m² vs. ≥ 25 kg/m²); and hormonal contraceptive use in females) and other baseline characteristics (inflammatory lesion counts, IGA score, and IGA scores for neck, chest, and back sites) will be summarized descriptively by treatment group for the Safety, ITT, and PP populations. Weight rounding for weight group is in the following way: 54.4 to 54, 54.5 to 55. Continuous variables will be summarized by number of subjects and mean, median, SD, minimum, and maximum values. Categorical variables will be summarized by number and percentage of subjects.

Comparability between treatment groups for efficacy variables will be tested using a 2-way analysis-of-variance model with treatment group and study center as the factors for continuous variables (inflammatory lesion counts and IGA score) and the CMH test, controlling for study center, for the categorical variable of IGA score. Because of their clinical importance, IGA score of the baseline characteristics will be treated as both a continuous and categorical variable.

Abnormalities in subjects' medical and surgical histories will be coded using the *Medical Dictionary for Regulatory Activities*, version 18.0 or newer. The number and percentage of subjects with abnormalities in medical and surgical histories in each system organ class and preferred term will be summarized by treatment group and overall for the Safety Population.

Prior medications including acne medications are those medications with an end date before the date of the first dose of investigational product. Concomitant medications including acne medications are those medications with either 1) a start date that is after the first dose of investigational product, 2) a start date prior to the first dose of investigational product with end date on or after the date of first dose of investigational product, or 3) a start date prior to the first dose of investigational product and its use is ongoing. Any concomitant medications taken after the date of the last visit will not be presented in the summary tables but will be included in the subject data listings.

Both prior and concomitant medications will be coded by drug preferred name and therapeutic class. The use of prior and concomitant medications and the use of prior and concomitant acne medications will be summarized by the number and percentage of subjects in each treatment group and overall for the Safety Population. If a subject took a specific medication multiple times or took multiple medications within a specific therapeutic class, that subject would be counted only once for the coded drug preferred name or therapeutic class.

The World Health Organization (WHO) Drug Dictionary, version March 2015 or newer, will be used to classify prior and concomitant medications by WHO Drug Anatomical/Therapeutic/Chemical category and WHO Drug preferred name.

9.0**EXTENT OF EXPOSURE AND TREATMENT COMPLIANCE****9.1****EXTENT OF EXPOSURE**

Exposure to the investigational product for the Safety Population during the double-blind treatment period will be summarized for treatment duration, calculated as the number of days from the date of the first dose of the investigational product to the date of the last dose of the double-blind investigational product, inclusive. Descriptive statistics (number of subjects, mean, SD, median, minimum, and maximum) will be presented by treatment group. Additionally, these summaries will present the number and percentage of subjects for each interval (1 week multiples) of total exposure in each treatment. The denominators for calculating the percentages will be based on the number of subjects with exposure for each treatment.

Subjects in the PK Schedule 3 group who receive one active dose of study drug after study assessments at Week 12 will also be listed (separately) for this single-dose exposure.

9.2**MEASUREMENT OF TREATMENT COMPLIANCE**

Dosing compliance for a specified period is defined as the number of tablets actually taken by a subject during that period divided by the expected number of tablets taken for the same period multiplied by 100. This information will be obtained from the drug accountability of the subject's eCRF. The total number of tablets actually taken will consist of subtracting both the total numbers of tablets returned and the total numbers of tablets lost from the total number of tablets dispensed. The number of tablets expected to be taken for a specific treatment period will be calculated based on the number of days in that period. Descriptive statistics for dosing compliance will be presented by treatment group for the whole double-blind treatment period for the Safety Population.

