16.8.1 Incomplete Start Date

The following rules will be applied to impute the missing numeric fields for an incomplete prior or concomitant medication start date. If the stop date is complete (or imputed) and the imputed start date is after the stop date, the start date will be imputed using the stop date.

Missing month and day

- If the year of the incomplete start date is the same as the year of the first dose of the investigational product, the month and day of the first dose of the investigational product will be assigned to the missing fields

- If the year of the incomplete start date is before the year of the first dose of the investigational product, *December 31* will be assigned to the missing fields
- If the year of the incomplete start date is after the year of the first dose of the investigational product, *January 1* will be assigned to the missing fields

Missing month only

- If only the month is missing, the day will be treated as missing and both the month and the day will be replaced according to the above procedure

Missing day only

- If the month and year of the incomplete start date are the same as the month and year of the first dose of the investigational product, the day of the first dose of the investigational product will be assigned to the missing day
- If either the year of the incomplete start date is before the year of the date of the first dose of the investigational product or if both years are the same but the month of the incomplete start date is before the month of the date of the first dose of the investigational product, the last day of the month will be assigned to the missing day.
- If either the year of the incomplete start date is after the year of the date of the first dose of the investigational product or if both years are the same but the month of the incomplete start date is after the month of the date of the first dose of the investigational product, the first day of the month will be assigned to the missing day

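### SAP 8.0 leaves a medication that starts on the first-dose date neither prior nor concomitant, contrary to Protocol 11.7.2, and SAP 16.8.1 imputes some partial start dates to exactly that day

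*SAP*

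**What the plan says.** SAP Section 8.0 defines both classes by dates relative to the first dose.

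- Prior: "Prior medications including acne medications are those medications with an end date before the date of the first dose of investigational product".
- Condition 1 for the concomitant class: "a start date that is after the first dose of investigational product".
- Condition 2 for the concomitant class: "a start date prior to the first dose of investigational product with end date on or after the date of first dose of investigational product".
- Condition 3 for the concomitant class: "a start date prior to the first dose of investigational product and its use is ongoing".

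The section then tabulates prior and concomitant medications, and separately prior and concomitant acne medications, for the Safety Population.

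Protocol 11.7.2 draws the line one day earlier. Its concomitant class opens with "Medications with a start date occurring on or after the first study drug dose date in the treatment period".

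SAP 16.8.1 fills in partial start dates. If month and day are missing and the year is that of the first dose, "the month and day of the first dose of the investigational product will be assigned to the missing fields". If only the day is missing and month and year are those of the first dose, "the day of the first dose of the investigational product will be assigned to the missing day". Other partial dates go to 31 December, 1 January, or the last or first day of the recorded month. If the imputed start falls after the stop date, the stop date replaces it.

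SAP 6.4 lists, as condition 2 for exclusion from the per-protocol population, "Have taken any interfering concomitant medications".

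**The concern.** The two SAP classes should between them cover every recorded medication. They do not: the boundary day is missing from the concomitant class and cannot belong to the prior class. The protocol has no such gap, and the SAP gives no reason for narrowing the rule. The SAP's own adverse-event rule in Section 11.1 does include the first-dose date, so the omission looks like a drafting slip.

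On its own the gap would touch only drugs actually started on Day 1. The imputation rule widens it, because two of its branches place uncertain start dates on the one day that the definition omits. An ongoing medication for which only the dosing year was recorded is a clear example: concomitant under the protocol, absent from both SAP tables.

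At stake is the completeness of the medication summaries. A secondary question is whether the per-protocol population, used in planned sensitivity analyses of both co-primary endpoints (SAP 10.1.1 and 10.1.2), could also be affected.

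**Working it through.** The plan states no figure on this point, so the check is one of date logic. Let F be the first-dose date, S the start date and E the stop date (or ongoing).

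**Rules as coded**

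- SAP 8.0: prior if E < F. Concomitant if S > F, or S < F and E ≥ F, or S < F and ongoing.
- Protocol 11.7.2: prior if E < F. Concomitant if S ≥ F, or S < F and either ongoing or E ≥ F.

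**Step 1: the boundary day.** Put S = F. A stop date cannot precede the start, so E ≥ F or the drug is ongoing, and the prior rule fails. S > F is false, and so is S < F, so all three SAP concomitant conditions fail. Under the protocol S ≥ F is true and the drug is concomitant.

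**Step 2: complete dates on a grid.** Start days run from 60 days before F to 90 days after it (151 values). Each start is paired with a stop 0 to 60 days later, or ongoing (62 options). That gives 151 × 62 = 9,362 records.

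| Rule | Concomitant | Prior | Unclassified | Total |
|---|---|---|---|---|
| SAP 8.0 | 7,470 | 1,830 | 62 | 9,362 |
| Protocol 11.7.2 | 7,532 | 1,830 | 0 | 9,362 |

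All 62 unclassified records have S = F, and 7,532 − 7,470 = 62. The prior count can be checked by hand: a start k days before F has k stop dates before F, and 1 + 2 + … + 60 = 60 × 61 / 2 = 1,830. The grid shows where the gap lies. It does not estimate how many medications are affected.

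**Step 3: partial start dates.** Take F = 15 June 2015 for illustration.

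| Recorded start | Stop | Start after 16.8.1 | SAP 8.0 | Protocol 11.7.2 |
|---|---|---|---|---|
| 2015 only | ongoing | 15 June 2015 | neither | concomitant |
| 2015 only | 20 July 2015 | 15 June 2015 | neither | concomitant |
| 2015 only | 10 June 2015 | 10 June 2015 | prior | prior |
| June 2015 | ongoing | 15 June 2015 | neither | concomitant |
| June 2015 | 15 June 2015 | 15 June 2015 | neither | concomitant |
| June 2015 | 10 June 2015 | 10 June 2015 | prior | prior |
| May 2015 | ongoing | 31 May 2015 | concomitant | concomitant |
| July 2015 | ongoing | 1 July 2015 | concomitant | concomitant |
| 2014 only | ongoing | 31 December 2014 | concomitant | concomitant |
| 2016 only | ongoing | 1 January 2016 | concomitant | concomitant |

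The two rules differ only where the start is imputed to F. That needs a match on year (month and day missing) or on month and year (day missing), and no earlier stop date.

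**Step 4: the per-protocol link.** SAP 8.0 applies its definition to Safety Population tables. SAP 6.4 does not refer to Section 8.0, gives no start-date rule for condition 2, and does not say how the list of affected subjects is produced. The link can be neither confirmed nor excluded from the text.

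**The case against.** **Time of day.** Condition 1 refers to the first dose, whereas condition 2 refers to its date. A drug begun later on Day 1 could therefore be said to start after the dose. This does not close the gap. Protocol 9.4.6 has medications recorded by date of initiation and discontinuation, and an imputed date carries no clock time.

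**Intent.** SAP Section 4.0 presents the SAP as an elaboration of the protocol, so a programmer could recover the intended rule from Protocol 11.7.2. That is fair and keeps the point minor. It would still mean departing from the SAP text without documentation.

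**The per-protocol check.** A reader might infer that these drugs also vanish from per-protocol condition 2. The documents do not support that as a fact, for the reason in Step 4. Protocol 11.2 names receipt of an excluded concomitant treatment as a possible major deviation, without a start-date rule. There are other routes to exclusion too. Use of another acne treatment may breach inclusion criterion IN07 or the washout required by EX04, which can bring the subject under condition 1. A subject discontinued under Protocol 9.4.6 because an excluded medication was needed would fall under condition 3. A Clinical Representative also reviews the list before unblinding. One reservation stands: the list is created first and then reviewed, so a subject who never reaches it may not be looked at. The loss would follow only if condition 2 is programmed from the Section 8.0 definition.

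**Loss of data.** A reader might also infer that all uncertain start dates are caught, or that the records themselves are lost. Neither is so. Only the two branches in Step 3 are involved, and nothing in the SAP removes the records from the data listings.

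**Conclusion.** The rule is wrong as written, and the consequence is minor. What is certain, on a calendar-date reading, is that Day 1 starts and the partial dates imputed to Day 1 fall outside both SAP classes and so outside both sets of summary tables, acne-medication tables included. An effect on the per-protocol sensitivity analyses is conditional on a programming choice that the SAP does not state. The intent-to-treat co-primary analyses do not use the definition and are unaffected. The documents do not say how many subjects have such records; the number is probably small.

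**What to change.** In SAP Section 8.0, reword condition 1 so that it covers a start on or after the date of the first dose, matching Protocol 11.7.2. With that rule every record in the grid is classified, and each partial date imputed to Day 1 becomes concomitant. SAP 16.8.1 needs no change.

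Optionally, add a sentence to SAP 6.4 saying that the list for condition 2 is drawn from all recorded on-treatment medications. That would settle the per-protocol question.

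The cost is a few words in the SAP. Data collection, study conduct and the intent-to-treat analyses are not touched.
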